Research Design. The proposed intervention will recruit 15 children with PMS and 15 children with iASD (2-12 years old). Treatment will follow a randomized, placebo-controlled, crossover format with 12 weeks in each treatment phase (rhGH and placebo). This duration was selected based on evidence with IGF-1 in PMS suggesting our clinical outcomes will be sensitive to change within this time frame (Kolevzon et al., 2014). The primary electrophysiological outcomes will be VEP gamma band activity as our preliminary data with PMS in IGF1 suggests it is sensitive to drug effects (Fig. 5). The primary clinical outcome will be the SAND because: a) our preliminary studies suggest improvement on this measure following IGF-1 (Fig. 6), b) it accurately reflects a sensory phenotype characteristic of PMS and is relevant to a substantial subset of iASD, c) it is associated with electrophysiological measures, and d) it has been validated in ASD and ID.

Inclusion criteria: All participants with PMS will have pathogenic *SHANK3* deletions or sequence variants confirmed in clinical genetics laboratories approved by the Clinical Laboratory Improvement Amendments (CLIA). Genotyping will also be used to confirm the absence of known pathogenic copy number variants in the iASD group. Participants with iASD will meet gold standard diagnostic criteria for ASD, confirmed by the Autism Diagnostic Observation Schedule – 2nd Edition (ADOS-2; Lord et al., 2012) and the Autism Diagnostic Interview-Revised (ADI-R; Lord et al., 1994). All iASD subjects will have a reduced neural response defined by $P_{60}-N_{75}$ amplitudes within one standard deviation of the PMS mean. Subjects will be on stable medication and psychosocial treatment regimens for at least three months prior to enrollment.

Exclusion criteria: 1) closed epiphyses; 2) active or suspected neoplasia; 3) intracranial hypertension; 4) hepatic insufficiency; 5) renal insufficiency; 6) cardiomegaly/valvulopathy; 7) allergy to growth hormone or any component of the formulation; 8) comorbid conditions which prevent participation; 8) visual problems which preclude use of VEP.

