Primary clinical outcome: SAND hyporeactivity subscale (Siper et al., 2017). Secondary and exploratory outcomes targeting ASD symptom domains: ABC-SW (Aman et al., 1985) and other measures employed in Aim 1 (Table 1) based on results from Aim 1. Clinical outcomes will be measured by an independent evaluator who is blind to side effects to prevent the risk of bias, and, within subjects, the same evaluator will complete assessments across all visits. Electrophysiological markers and clinical measures will be collected at baseline, weeks 4, 8, and 12 of each phase. Safety and tolerability will be measured after two weeks in each phase and then

every four weeks thereafter during monitoring visits and phone calls using an adapted semi-structured interview, the Safety and Monitoring Uniform Report Form (SMURF); extensive clinical

Table 1: Clinical Outcome Measures		
Domain	Instrument	Measurement modality
Social	Aberrant Behavior Checklist - Social Withdrawal Subscale	Caregiver report
Language /Communication	MacArthur-Bates Communication Development Inventory Vineland Adaptive Behavior subscales Mullen Scales for Early Learning subscales	Caregiver report Caregiver report Direct assessment
Repetitive Behavior	Repetitive Behavior Scales-Revised Aberrant Behavior Checklist - Motor Stereotypies Subscale Sensory Profile Sensory Assessment for Neurodevelopmental Disorders	Caregiver report Caregiver report Caregiver report Direct assessment
Adaptive Behavior	Vineland Adaptive Behavior Scales-3	Caregiver report

and laboratory

assessments will occur every four weeks during visits (see Protection of Human Subjects).

Language testing will include standardized measures reliant on caregiver report and objective standardized assessments. Specifically, caregivers will report on a child's expressive and receptive verbal and non-verbal communication repertoire on the MacArthur-Bates Communication Development Inventory (MCDI; Fenton et al., 2007), which is a valid assessment of young children's language (Charman et al., 2003; Luyster et al., 2007). Although not normed in children above 30 months of age, preliminary data collected on this measure suggest that raw scores on the MCDI are useful in capturing the range of language functioning in our minimally verbal and intellectually disabled sample. The MSEL and Vineland will provide standardized assessments of receptive and expressive language, by direct assessment and parent interview, respectively.

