Data Analysis. Following the procedures of a 2x2 cross-over design, each subject is randomized to one of two treatment sequences. First we will use graphical and numerical statistics to characterize treatment-, period- and cross-over effects (Jones & Kenward, 1989). Under the assumption of no cross-over effects and data following an approximate normal distribution, we will fit generalized linear mixed models (GLMMs) to the data examining the effects of group (PMS, iASD), condition (placebo, drug), time (baseline, week-12). Interactions on clinical and VEP measures will be checked for differential treatment effects, including subject level random

intercepts, to control for within subject correlations. Next, we will add baseline VEP gamma band activity, along with its interactions, to the models for clinical outcomes. In particular, a VEP by group by time interaction would suggest that the electrophysiological marker is predictive of differential treatment response. We will repeat these analyses with secondary electrophysiological markers and any derived composites. To examine whether electrophysiological markers track changes in clinical profiles, we will fit an additional GLMM with VEP values included as a time-varying rather than baseline covariate. If treatment effects become less significant it will suggest that rhGH is acting on clinical outcomes through the biomarker. Finally, we will directly correlate week-12 change scores for EEG and clinical measures. In case of major cross-over effects, we will base our primary analysis on phase 1 data only as a parallel group study. All tests will use a two-sided α of .05.

Power Analysis: Power is calculated for drug group differences in baseline to week 12 change scores in VEP gamma power since we are primarily interested in an overall treatment effect rather than a differential effect by group. These correspond to paired t-tests, taking advantage of the crossover design. With α at .05, we have 80% power to detect moderate to large effects ($d=.77$ within each group, $d=.53$ across groups), a reasonable expectation based on the potentially disease modifying effects of IGF-1 and our pilot study, which found a large effect ($d=1.05$) of IGF-1 in PMS on a different primary outcome (ABC-SW).

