Potential pitfalls and alternative strategies. We expect loss of some electrophysiological data due to the severely affected nature of the population; however, this study is well powered and our proposed sample size can accommodate attrition and still detect meaningful differences across a range of responses. We have been successful in recording VEP in more than 70% of patients with PMS seen in our center. We will implement a sensory desensitization and behavioral training protocol and have extensive experience collecting these data from children with ASD, PMS, and severe ID. Moreover, for the VEP, short-duration stimulus conditions are being utilized. In addition, crossover trial designs carry risks of contamination effects, so we have provided a four-week washout period to minimize this risk. We have not observed significant carryover effects in our preliminary data. We believe this design is important because all patients will be afforded the opportunity to receive active medication. Second, the burden of frequent monitoring visits and subcutaneous injections risks increase the risk of subject withdrawal. Given the rigid control of the study procedures, relatively simple measurement techniques, and based on our experience to date, we do not foresee any major loss of data due to drop-outs or missing values. Still, in case of drop-outs we will use the intent to treat principle so all randomized patients will be included in the data analysis. Third, because of concerns about recruitment feasibility, we have established an excellent working relationship with the national PMS Foundation. Fourth, because we are only enrolling patients with iASD with PMS-like VEP amplitudes, we will not be able to test the *specificity* of target engagement and successful treatment response. Finally, if VEPs cannot be established as a biomarker for stratification or efficacy, we still have a wealth of other electrophysiological and clinical outcomes that will provide critical information.

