- Laboratory: any abnormality on any test with adverse event (AE, Common Terminology Criteria for Adverse Events, National Cancer Institute, scales) ≥ 3 or greater at any time in the study
- Any AE of any sort (clinical, laboratory) ≥ 4 will result in halting for the individual and also for the study as a whole.

To avoid bias, all analyses will include all subjects, including those withdrawn from the study, regardless of adherence to study protocol. Especially in an exploratory trial of a novel, unproven treatment, the safety of subjects is our primary *overriding* concern. If there is doubt concerning a subject's safety, the default mode will be withdrawal from treatment or active study participation, followed by close observation (safety follow up visits) and recommendation of standard treatment.

Return of a subject to active study participation will not be permitted, except if a transient clinical or laboratory abnormality unrelated to study treatment has occurred and subsequent permission of the Safety Monitoring Board to return the patient to active study has been provided.

If a subject is withdrawn from active study during screening or observation phases of the study, they will be returned to the referring physician and standard care will be recommended; in addition we will request the subject's participation in an end-of-study visit.

If a subject is withdrawn from active study during rhGH treatment, they will also be returned to the referring physician and standard care will be recommended; however, in this case, we will in addition request the subject's participation in clinical and laboratory safety assessments and follow up per protocol schedule.

Stopping Conditions for Study as a Whole

The study will be halted* if two patients experience stopping conditions. (Exceptions for this criterion: Patients who withdraw voluntarily for reasons not directly related to or intrinsic to the study, e.g. incidental considerations such as concerns about travel time to study visits, unexpected pregnancy in the family, etc. Clearly, patients who experience adverse effects during rhGH treatment would count towards this criterion for whole study stopping).

In addition, the study will be halted if one patient experiences a serious related adverse effect (grade \geq 4 AE).

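### The treatment model uses only baseline and week 12 with a subject random intercept, so weeks 4 and 8 cannot protect the week-12 contrast when a week-12 value is missing

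*Combined protocol and SAP*

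**What the plan says.** All references are to the combined protocol and SAP.

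- **Design (Research Design).** "Treatment will follow a randomized, placebo-controlled, crossover format with 12 weeks in each treatment phase".
- **Visits (Outcome measures).** "Electrophysiological markers and clinical measures will be collected at baseline, weeks 4, 8, and 12 of each phase".
- **Model (Data Analysis).** Mixed models "examining the effects of group (PMS, iASD), condition (placebo, drug), time (baseline, week-12"). On covariance: "Interactions on clinical and VEP measures will be checked for differential treatment effects, including subject level random" intercepts. No other within-child correlation is named.
- **Drop-outs (Potential pitfalls and alternative strategies).** "in case of drop-outs we will use the intent to treat principle so all randomized patients will be included in the data analysis". The same section expects that "we do not foresee any major loss of data due to drop-outs or missing values", although it also expects some loss of electrophysiological data and names visit and injection burden as a withdrawal risk.
- **Withdrawn children (Stopping Conditions for Individual Subjects).** "To avoid bias, all analyses will include all subjects, including those withdrawn from the study, regardless of adherence to study protocol". For a child withdrawn during rhGH, the team will "request the subject's participation in clinical and laboratory safety assessments and follow up per protocol schedule". VEP and SAND are not named there.

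The documents give no dropout rate, missing-data method, missingness assumption or sensitivity analysis. Weeks 4 and 8 are not used to estimate the drug effect. The Aim 3 summary mentions only exploring VEP by time point in relation to dose and IGF-1 level.

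**The concern.** With two time levels, a phase that lacks its week-12 value enters the model as a baseline alone. This happens when a child withdraws, and also when a child stays in the trial but the week-12 recording fails. A child who leaves in phase 1 and does not return contributes a single baseline value and nothing on drug versus placebo, even if week 4, or weeks 4 and 8, were recorded.

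The model is then valid only if a missing week-12 value is unrelated to how the child was doing at weeks 4 and 8, given the values that remain in it. A likelihood model that holds the interim visits and describes their correlation with week 12 adequately needs a weaker assumption, because missingness may then depend on that observed course. At stake is the week-12 contrast for gamma MSC and SAND hyporeactivity, the primary electrophysiological and clinical outcomes.

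**Working it through.** **1. The plan's own figure.** The Power Analysis section uses paired t-tests on baseline to week-12 change, two-sided α of .05. Power is P(T > t(0.975, n−1)), where T is noncentral t with n−1 degrees of freedom and noncentrality d√n; the opposite tail is negligible.

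- n = 15, d = 0.77: 79.2%.
- n = 30, d = 0.53: 80.1%.

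The stated 80% reproduces, on the premise that every child has week 12 in both phases. In a paired analysis with 10%, 20% or 30% of the 30 children lacking this (n = 27, 24, 21), power at d = 0.53 is 75.5%, 70.1% and 63.7%. The planned mixed model keeps single completed phases, so these are rough figures for it.

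**2. Bias in a trial of this size.** All inputs here are assumed, because the documents give none: 30 children; a 2x2 crossover; total variance 1, half of it between children; AR(1) correlation of 0.5 or 0.7 between successive visits within a phase; true week-12 effect 0.50. Withdrawal comes after week 8 and is likelier when the week-8 change is poor (logit = −(2.0 + 2 × week-8 change)). Drug-phase dropout is about 12 to 14%. The baseline and week-12 model gave:

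| Withdrawal | Mean estimate (true 0.50) |
|---|---|
| Response-related on rhGH only, 5% at random on placebo | about 0.54 to 0.56 |
| Same response-related rule in both phases | about 0.47 to 0.50 |
| Completely at random | about 0.49 to 0.50 |

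The first row is a bias of 0.04/0.50 = 8% to 0.06/0.50 = 12% upward. The second runs from none to 0.03/0.50 = 6% downward. Against an empirical standard error of about 0.19, the largest shift is 0.06/0.19 = 0.3 standard errors.

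**3. What removes the bias.** In the rhGH-only case, adding weeks 4 and 8 under the random intercept alone still gave about 0.53 to 0.54. Adding them with an adequate within-phase correlation gave 0.495 to 0.498.

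A second, large-sample simulation separates the two changes. It assumed 40,000 children, child-specific slopes, a true effect of 0.53 outcome units (not the plan's standardised d), dropout dependent on change by week 8, and placebo dropout at one quarter of the drug-phase rate:

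| Model | 10% | 20% | 30% drug-phase dropout |
|---|---|---|---|
| Baseline + week 12, random intercept (as planned) | 0.617 | 0.679 | 0.731 |
| Baseline + week 12, unstructured | 0.627 | 0.690 | 0.750 |
| All visits, random intercept | 0.610 | 0.665 | 0.711 |
| All visits, unstructured | 0.537 | 0.530 | 0.518 |

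The planned model is off by 0.617/0.53 = 1.16, 0.679/0.53 = 1.28 and 0.731/0.53 = 1.38. Neither change works alone; together they bring the estimate within about 2%. With dropout completely at random, all four models gave 0.52 to 0.54.

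**4. Cost in precision.** In the 30-child set-up, two visits and four visits had almost the same empirical standard error when the covariance was taken as known (0.190 and 0.189 in one setting, 0.182 and 0.179 in the other). Estimating a full unstructured 8x8 matrix over both phases widened it from about 0.19 to 0.22.

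**The case against.** Week 12 is the time point used for power, and analysing it directly is an accepted choice in a 30-child feasibility study whose sponsor expects little loss. The interim visits add almost no precision. These points stand, and they are why the primary contrast should stay at week 12. They do not supply a missing-data assumption, and an expectation of little loss is not a plan for handling it.

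Three stronger readings are tempting, and the documents do not support them.

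- *The drug effect will be overstated.* This needs response-related withdrawal on rhGH but not on placebo. The trial is double-blind, and the visit and injection burden that the plan names falls on both phases. Under the same rule in both phases the bias is small and, if anything, conservative. Safety stopping could create an asymmetry, but most laboratory tests in Table 2 are scheduled only at baseline and week 12, which limits that route in mid-phase.
- *The intent-to-treat promise is empty.* Children are analysed regardless of adherence, and a child who leaves in phase 2 keeps a complete phase 1. Follow-up is requested after withdrawal during rhGH, so collection of VEP and SAND at week 12 is unclear rather than excluded. Inclusion is only nominal for a phase-1 withdrawal with no later outcome data.
- *Weeks 4 and 8 are both available for anyone who leaves before week 12.* A child who leaves in weeks 5 to 7 has week 4 only.

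**Conclusion.** The point holds as a cheap improvement to the analysis. The plan leaves out of its treatment model measured data that would support a weaker missingness assumption, and it states no assumption of its own.

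The direction and size of any bias cannot be read from the documents. At the assumed 12 to 14% drug-phase dropout it ranges from about 6% downward to 12% upward, depending on whether withdrawal is response-related in one phase or both, and it is nil if missingness is completely at random. The larger figures in the second simulation (16% to 38%) rest on steeper assumptions, including child-specific slopes and dropout of up to 30%. The time factor is only half of the problem: with the planned random intercept alone, extra visits leave most of the bias in place.

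**What to change.** In Data Analysis, for gamma MSC and SAND hyporeactivity:

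1. Include baseline and weeks 4, 8 and 12 of each phase, with categorical time by condition and period terms.
2. Keep the subject random intercept and add a named, parsimonious within-phase residual correlation, such as heterogeneous Toeplitz or AR(1). Name a simpler fallback in case the model does not converge. Avoid a full unstructured matrix over both phases.
3. Keep the week-12 drug-placebo contrast as the primary test.
4. State the missing-at-random assumption and add one sensitivity analysis that departs from it, for example by shifting the missing week-12 values.

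The cost is wording and a few more covariance parameters estimated in 30 children. The scheduled visits, the outcomes and the primary time point do not change. Little gain in precision should be expected, and the change will not restore the power lost if week-12 data are missing.

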Through completion of Aims 1 and 2, we have: 1) validated the ASD phenotype within a sample of individuals with PMS, 2) established electrophysiological biomarkers of PMS, and 3) used biomarkers associated with PMS to identify an overlapping subset in iASD. In Aim 3, we will evaluate the feasibility of our biomarkers in a clinical trial with rhGH. Results will demonstrate evidence of our biomarkers' utility for: 1) stratifying subsets within iASD, 2) detecting target engagement with rhGH via neural responses, and 3) predicting treatment responders based on electrophysiological profiles. We have demonstrated feasibility of our biomarkers in individuals with ID who are minimally verbal, and this study will specifically focus on this underserved population in ASD research. *Upon successful completion of the proposed research*, we expect to clarify an underlying neural mechanism in PMS common to subsets of iASD, validate methods to predict treatment response for future clinical trials, and demonstrate efficacy of rhGH for individuals with PMS and iASD with glutamatergic dysfunction.

Innovation

To date, the development of treatments in ASD has mainly relied on strategies only loosely related to what is known about the neurobiology, using etiologically heterogeneous samples, and delivering intervention broadly and with mixed success. More recently, genetic discovery and model systems have elucidated the neurobiology of several subtypes of ASD, including PMS, and led to opportunities for developing biomarkers and novel therapeutics. *This proposal is innovative, in our opinion, on several technical and conceptual levels.* First, this study will leverage existing work in animal models of PMS and include electrophysiological tests. Second, we have the largest known cohort of individuals with PMS and have identified both a unique clinical phenotype and a striking VEP deficit that characterizes this population. Thus, we are uniquely situated to systematically assess the reliability of both clinical and electrophysiological measures in PMS. Third, the phenotype and electrophysiological profile identified in PMS is critically relevant to ASD. We will use the knowledge gained in an ASD-related syndrome to inform stratification of a subset

Figure 6. Children with PMS show significant improvement in sensory symptoms following 12 weeks of treatment with IGF-1. Greatest improvement was noted in the hyporeactivity domains ($n=6$);

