of iASD with constrained heterogeneity based on a biological marker. Fourth, given our strong preliminary data in PMS and iASD and existing infrastructure and pipeline for conducting clinical trials, we will test the feasibility and robustness of electrophysiological markers in the context of treatment with rhGH, a step which has yet to be taken successfully in the ASD literature. Fifth, we expect to predict a subset of iASD with high potential to respond to treatment with rhGH based on biological profiles related to PMS, making progress toward a more personalized medicine approach for ASD.

Approach

Aim 3: Evaluate the feasibility of electrophysiological markers as a measure of treatment response.

Introduction. The objective of this aim is to administer rhGH to participants with PMS and iASD to evaluate the feasibility of select electrophysiological biomarkers to: 1) detect change in neural response (engagement) and 2) predict treatment responders on clinical assessments (efficacy). We will also explore the relationship between rhGH dose, IGF-1 level, and electrophysiological response. Participants will be selected based on electrophysiological profiles with reduced $P_{60}-N_{75}$ VEP amplitudes, reflecting impaired glutamatergic function. **Approach:** We will employ a randomized, placebo-controlled, double-blind, crossover design with a four-week wash-out period between phases. **Rationale:** Successful completion of this aim will establish feasibility of select biomarkers for detecting treatment response and advance knowledge about developing targeted treatments for PMS and related subsets of iASD with impaired glutamatergic activity. We expect, based on preliminary data, that the knowledge gained will provide evidence of targeted brain engagement with rhGH, a mechanistic pathway, and evidence of clinical efficacy.

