Expected outcomes. We expect to provide evidence for the feasibility of using VEPs to detect neural change related to glutamatergic activity in response to treatment with rhGH. Specifically, we expect rhGH will be associated with increased low gamma band activity as compared to placebo in both PMS and the PMS-like iASD subset. We further anticipate enhanced gamma band activity to be associated with changes on clinical outcome measures, particularly those that reflect sensory reactivity given our preliminary data. Finally, we expect to demonstrate that rhGH treatment will result in changes on primary and secondary outcomes of sensory reactivity, social impairment, repetitive behavior, and functional outcomes of adaptive behavior. *If positive, in addition to demonstrating efficacy of rhGH for PMS, results from this clinical trial will demonstrate the feasibility of using electrophysiological markers to stratify patients with iASD and identify early biomarkers of potentially disease-modifying effects on core symptoms of ASD.*

Timeline

It is anticipated that 30 months will be required to complete Aim 3. Months 0-4 will be dedicated to study startup, regulatory, and Review Board approval. Months 5-20 will be required to enroll 30 participants (15 PMS; 15 iASD) at a rate of 1 participant per group per month. Months 21-27 will be required to complete data collection and months 28-30 will be reserved for data analysis. This timeline is considered feasible based on our experience and assessment of current interest among families on our waiting list and registered with the PMS Foundation.

Protection of Human Subjects

Risks to the Subjects

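### The interaction the plan reads as VEP predicting response to rhGH (VEP by group by time) leaves out the treatment factor

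*Combined protocol and SAP*

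**What the plan says.** The combined protocol and SAP (Approach, Aim 3, Data Analysis) sets up mixed models "examining the effects of group (PMS, iASD), condition (placebo, drug), time (baseline, week-12"). Diagnosis and treatment are therefore two separate factors with their own names. The text continues: "Next, we will add baseline VEP gamma band activity, along with its interactions, to the models for clinical outcomes". The interactions are not listed, but one is singled out for interpretation: "a VEP by group by time interaction would suggest that the electrophysiological marker is predictive of differential treatment response". The same analyses are then to be repeated for the secondary electrophysiological markers and any composites. No section names an interaction between VEP and condition.

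The Power Analysis uses the word group in two ways. It begins "Power is calculated for drug group differences in baseline to week 12 change scores in VEP gamma power", where the word refers to treatment, and then says the investigators are "primarily interested in an overall treatment effect rather than a differential effect by group", where it refers to diagnosis.

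Prediction is a stated purpose. The Introduction to Aim 3 gives as its second objective to "predict treatment responders on clinical assessments (efficacy"), and the Significance section lists "predicting treatment responders based on electrophysiological profiles" among the expected results.

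**The concern.** A marker predicts response to rhGH if the drug-placebo difference in change depends on the baseline value of the marker. A test of that must involve condition, and the named term does not. Two errors follow.

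- **Missed prediction.** A marker that works alike in PMS and iASD contributes nothing to a contrast between the diagnoses. This is a natural case under the plan's premise that the selected iASD children share the altered pathway with PMS. Expected outcomes also anticipates "increased low gamma band activity as compared to placebo in both PMS and the PMS-like iASD subset". That is a statement about the mean effect on gamma, so it does not itself assert equal prediction, but it does not point to a diagnosis-specific mechanism either.
- **False prediction.** If VEP-related change over 12 weeks differs between the diagnoses for reasons unrelated to drug (development, practice, regression to the mean), the named term can be significant and would be read as prediction of response.

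What is at stake is one of the two stated purposes of Aim 3, and the error carries over to each secondary marker.

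**Working it through.** **1. The plan's own power figure.** For a paired t-test, two-sided α 0.05, the noncentrality is d√n.

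- Within a diagnosis: 0.77 × √15 = 2.98 on 14 df, power 79.2%.
- Across diagnoses: 0.53 × √30 = 2.90 on 29 df, power 80.1%.

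The stated 80% reproduces. It concerns the overall drug effect on VEP gamma change and covers no interaction.

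**2. What each interaction estimates.** Let β(g,c) be the slope of baseline-to-week-12 change on baseline VEP in diagnosis g (P = PMS, A = iASD) under condition c (drug, plac). With effect coding, and up to a scale factor:

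- VEP × group × time: ½[β(P,drug) + β(P,plac)] − ½[β(A,drug) + β(A,plac)]
- VEP × condition × time: ½[β(P,drug) + β(A,drug)] − ½[β(P,plac) + β(A,plac)]
- VEP × group × condition × time: [β(P,drug) − β(P,plac)] − [β(A,drug) − β(A,plac)]

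Suppose VEP predicts drug response with slope s in both diagnoses and nothing else is going on. Then β(P,drug) = β(A,drug) = s and the placebo slopes are 0. The first contrast is s/2 − s/2 = 0 and the second is s. Suppose instead VEP is unrelated to drug response but its slope differs by δ between diagnoses under both conditions. The first contrast is δ and the second is 0. Neither result depends on any effect size.

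**3. Size.** The documents give no slopes, so these are assumptions: residual SD 1, 15 + 15 children with complete data, and slopes in residual SD per SD of VEP. Change in one condition has SD √2, the drug-minus-placebo difference in change has SD 2, and the average change over conditions has SD 1. The largest slope, 1.06 = 0.53 × 2, borrows the plan's detectable effect for scale only.

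Approximate noncentralities:

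- Shared predictor, VEP × condition × time: s ÷ (2/√30). For s = 0.5 this is 1.37; for s = 1.06 it is 2.90.
- Non-drug difference δ, VEP × group × time: (δ/2) ÷ (1/√30). For δ = 0.5 this is 1.37; for δ = 1.06 it is 2.90.
- Correlation of VEP with the drug-placebo difference in change: s/√(s² + 4), which is 0.12, 0.24 and 0.47 for s = 0.25, 0.5 and 1.06.

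Percent significant at 0.05, from 6,000 simulated trials per scenario:

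| Scenario | VEP × group × time (named) | VEP × condition × time |
|---|---|---|
| No effect of VEP | 4.7 | 5.2 |
| Shared predictor, slope 0.25 | 4.6 | 9.3 |
| Shared predictor, slope 0.5 | 5.1 | 24.5 |
| Shared predictor, slope 1.06 | 4.7 | 73.7 |
| No prediction, non-drug difference 0.25 | 9.9 | 5.4 |
| No prediction, non-drug difference 0.5 | 24.6 | 4.6 |
| No prediction, non-drug difference 1.06 | 74.1 | 4.8 |
| Predictor in PMS only, slope 1.06 | 27.6 | 26.3 |

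The simulated rates sit a little below what the noncentralities imply because the spread of VEP among 15 children varies from trial to trial. A regression on change scores gives the same pattern: 4.6 and 23.2 for a shared slope of 0.5, and 23.5 and 5.2 for a non-drug difference of 0.5. A separate simulation (10,000 runs) gives 4.9 and 81.3 for a shared slope of 1.2, and 81.7 and 4.9 for a non-drug slope difference of 1.2.

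**4. Coding.** If the software takes placebo as the reference level in a full model, VEP × group × time is estimated from placebo data only. A PMS-only predictor of slope 1.06 is then flagged in 5.1% of trials, and a non-drug difference of 1.06 in 47.3%.

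**The case against.** Three arguments have weight.

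- **The word group may be a slip for treatment arm.** The Power Analysis uses it that way once, the fallback to first-phase data describes a comparison of parallel arms, and the sentence itself is about treatment response. On that reading the intended test is correct and the simulated error rates do not describe it. Against this, the model is defined a few lines earlier with group as diagnosis, and the power text relies on that meaning for its within-group and across-group effect sizes. An analyst who follows the definitions would test the wrong term, so the wording needs correcting even if the intention was sound.
- **The fitted model may already contain the right term.** The plan adds VEP with unspecified interactions to a model that includes condition and time, and the sentence highlights one interaction without excluding others. That is fair: the defect lies in the term chosen for interpretation, not necessarily in the model. But it is the only guidance on what counts as prediction, and choosing a different term after seeing the results would weaken any claim.
- **The effect sizes are assumed.** No document shows that VEP-related non-drug change differs by diagnosis, complete data are optimistic, and the corrected term has only 9% to 25% power at slopes of 0.25 to 0.5. This stands. The percentages illustrate the algebra and are not forecasts for this trial. The correction makes the test valid but does not make it powerful.

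One could also read differential as differing between diagnoses. That question needs VEP by group by condition by time. The named term does react to a PMS-only predictor (28%), but cannot tell it from non-drug change.

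**Conclusion.** The concern holds. Under the plan's own definitions, the interaction offered as evidence of prediction omits treatment. It has no power beyond the 5% error rate for a predictor shared by both diagnoses, whatever its strength. It can also be significant when VEP has no bearing on drug response: 10%, 25% and 74% of trials for non-drug slope differences of 0.25, 0.5 and 1.06. The direction of both errors follows from the contrasts alone. The percentages rest on assumed slopes, residual SD 1 and complete data on 30 children. Whether the authors meant treatment arm cannot be settled from the text, but the sentence needs changing on either reading. The overall treatment comparison and its stated power are unaffected. This should be fixed before analysis; it does not threaten the main comparison.

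**What to change.** Replace the sentence in Data Analysis with: *A baseline VEP by condition by time interaction tests whether the marker predicts response to rhGH; a VEP by group by condition by time interaction explores whether this differs between PMS and iASD.* Use the same terms when the analysis is repeated for secondary markers and composites, and reserve the word group for diagnosis throughout, including the Power Analysis. State that the 80% power applies to the overall treatment effect and not to these interactions. It would be sensible to label them exploratory, although that is the investigators' choice.

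The cost is one or two sentences before analysis, with no new data, no additional children and no change to sample size.
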